7.1.3 Product Storage and Stability

Influenza vaccines will be stored in secure, limited-access temperature monitored refrigerator environment at 2°C to 8°C (.6°F to 46°F) until needed. DO NOT FREEZE. The temperature of the storage unit will be monitored during the duration of the trial, and documentation of proper dedicated storage will be maintained. In the event of accidental deep-freezing or disruption of the cold chain, vaccines will not be administered; and the PI or the responsible person will contact the sponsor for further instructions.

7.2 Dosage, Preparation and Administration of Study Intervention/Investigational Product

Each of the vaccines used in this study will be formulated in single dose vials or syringes and will not require additional formulation prior to administration. A vaccine dose of 0.5mL will be administered by a clinical research nurse intramuscularly (IM) in the subject's preferred deltoid (upper arm) per the manufacturer's instructions.

7.3 Modification of Study Intervention/Investigational Product for a Participant

As there is only a single dose administered, there will be no dose or schedule modifications for any subject.

7.4 Accountability Procedures for the Study Intervention/Investigational Product(s)

Study vaccine will be sent to the research site at the University of Rochester prior to the start of the study. Records of vaccine receipt and dispensation to the study subject as well as storage and destruction of the vaccine will be maintained according to existing standard operating procedures (SOPs)

7.5 Assessment of Participant Compliance with Study Intervention/Investigational Product

Not applicable, single intervention within the vaccine clinic only.

7.6 Concomitant Medications/Treatments

Administration of any medication or therapies considered necessary for the subject's welfare will be recorded and documented in the subject's source documentation. Concomitant medications will include all medications taken within 30 days prior to enrollment through 56 days post vaccination or early termination, whichever occurs first.

The following criteria will be reviewed with the subject's during each follow up visit. If any of these become applicable during the study, it will be noted in the subject's record.

1. Use of any investigational drug or investigational vaccine other than the study article.
2. Administration of chronic (defined as more than 14 days) immunosuppressants or other immune-modifying drugs (topical and nasal steroids are allowed).
3. Receipt of a licensed vaccine.
4. Receipt of immunoglobulins and/or any blood products.

8 STUDY SCHEDULE

8.1 Screening (Day -21 to Day 0)

Subjects will be screened for eligibility and for vaccine history prior to group assignment and vaccination. At the screening visit, the following procedures will be performed:

- The study will be explained to the subject, and the informed consent document will be signed. Subjects will keep a copy of the informed consent for their information.
- A medical history will be obtained, and details recorded in the case report form.
- A directed physical examination will be performed, if indicated by the medical history, directed at the relevant portions of the exam.
- The entry criteria will be reviewed and it will be verified that the subject meets all entry criteria. If the subject does not meet the entry criteria, the subject will be discontinued from the study, or can be rescreened in the case of entry criteria mandating temporary delays.

8.2 Vaccination (Defined as Day 0)

Subjects will be considered enrolled if they have signed the consent form. However, only subjects who met the entry criteria will be vaccinated and followed. Note that the screening visit and the vaccination visit may take place on the same day. At the vaccination visit the following procedures will be performed.

- An interim medical history will be obtained (unless the screening and vaccination visit are the same) including concomitant medications, detailing any subsequent medical events the subject has experienced since the screening visit.
- A directed physical exam will be performed, if indicated by the interval history, directed at the relevant portions of the exam.
- A urine pregnancy test will be obtained in female subjects. This test must be negative for the subject to continue in the study.
- The entry criteria will be reviewed with the subject and it will be verified that the subject continues to meet the entry criteria.

- A serum sample will be obtained from an arm vein for baseline antibody titers
- A sample of Peripheral Blood Mononuclear Cells (PBMC) will be obtained for assessment of baseline influenza-specific B cells and CD4 cells
- Subjects that were not vaccinated with influenza vaccine with the prior year's vaccine, will be randomized at the pharmacy into one of the three (FluBlok, Fluzone SD, Fluzone HD) vaccine groups, and will receive the indicated vaccine by intramuscular injection in open label fashion.
- Repeat subjects will receive the same vaccine they received previously. (FluBlok, Fluzone SD, Fluzone HD, Flucelvax)
- Subjects will be observed in the clinic for 30 minutes post vaccination for development of acute adverse events

8.3 Follow-up and Final Visits

8.3.1 Day 3 visit ((± 1 day)

Subjects will return 3 days after vaccination for the first visit. Because the timing of assessment of the cellular response to vaccination is critical, every effort will be made to ensure that subjects return on day 3. On the day 3 visit, the following procedures will be done:

- Interval medical history will be obtained including concomitant medications, reviewing any new events since the last visit
- If indicated by medical history, a directed physical exam will also be performed.
- Any adverse events (AE) will be recorded as described in the safety section 10.1 and appropriate corrective actions taken if indicated
- Peripheral Blood Mononuclear Cells (PBMC) will be collected from an arm vein for assessment of the CD4 T cell response to vaccination

8.3.2 Day 7 visit (\pm 1 day)

Subjects will return one week after vaccination for the day 7 visit. Because the timing of assessment of the cellular response to vaccination is critical, every effort will be made to ensure that subjects return on day 7. On the day 7 visit, the following procedures will be done:

- Interval medical history will be obtained including concomitant medications, reviewing any new events since the last visit
- If indicated by medical history, a directed physical exam will also be performed.
- Any adverse events (AE) will be recorded as described in the safety section 10.1 and appropriate corrective actions taken if indicated
- Peripheral Blood Mononuclear Cells (PBMC) will be collected from an arm vein for assessment of the B cell and CD4 T cell response to vaccination

8.3.3 Day 14 visit (\pm 1 day)

Subjects will return for follow up approximately 14 days after vaccination for assessment of the immune response. At that visit, the following procedures will be performed.

- Interval medical history will be obtained including concomitant medications, reviewing any new events since the last visit. If indicated by history, a relevant physical exam will also be performed.
- Any adverse events (AE) will be recorded as described in the safety section 10.1 and appropriate corrective actions taken if indicated
- Peripheral Blood Mononuclear Cells (PBMC) will be collected from an arm vein for assessment of the CD4 T cell response to vaccination

8.3.4 Day 28 visit (\pm 2 days)

Subjects will return for follow up approximately 28 days after vaccination for assessment of the immune response. At that visit, the following procedures will be performed:

- Interval medical history will be obtained including concomitant medications, reviewing any new events since the last visit
-

-
- If indicated by medical history, a directed physical exam will also be performed.
 - Any adverse events (AE) will be recorded as described in the safety section 10.1 and appropriate corrective actions taken if indicated
 - A serum sample will be obtained from an arm vein for antibody titers
 - Peripheral Blood Mononuclear Cells (PBMC) will be collected from an arm vein for assessment of the B cell response to vaccination

8.3.5 Influenza surveillance

Influenza season will be defined as when community laboratories detect 4 or more positives in any one week for two weeks in a row, and will end when influenza is no longer detected. During influenza season, subjects will be asked to record weekly on a mobile device application (MyCAP) if they have developed influenza like symptoms.

MyCAP is a mobile app that interfaces with REDCap using REDCap's secure API. It gives researchers the ability to collect task oriented data on participants via the participants' mobile device in real time. Enrolling the participant and subsequently communication between the MyCAP mobile app and REDCap server is made possible by generating a unique QR code for each participant from the REDCap-MyCAP web portal. The mobile app scans this QR code which contains the project name, site and uniquely auto-generated participant id. The participant id is created by REDCap and is not based upon any data entered about the participant at any time or linked to any personal health information or identifying information. The mobile app and consequently the participant, only have the capability of submitting data to the project, eliminating the concern of data breaches since there is no capability to view or read any data from the project. The app will also have the capability to be password protected.

Once the mobile app has registered the QR code, participants will be asked to answer a weekly survey which they will be prompted to complete every Tuesday pertaining to the development of influenza like illness and associated symptoms. Data collected from participants in the mobile application will only be available to study staff. The following questions will be asked:

1) Have you had a fever or felt feverish in the past 5 days?

- yes no

2) Have you had any of the following symptoms in the past 5 days: runny nose, cough, sore throat, body aches?

- yes no

Subjects who do not have a mobile device compatible with the application or are unable or unwilling to utilize the application will be called weekly by the study staff and queried using the aforementioned questions. The app will send a reminder to study subjects at on Tuesday morning of every week to complete the surveillance questions. While there is no window built into the app for subjects to complete these questions it will be expected that they respond to the questions within 24 hours. Questions can only be answered once a week. If questions were not completed for the week the study team will be notified and this will be reviewed on Monday of the following week. If a subject misses two consecutive surveillance time points, the study team will call them to determine if there is an issue with the app or alternatively if they would prefer phone surveillances be conducted. If it is the latter case, the app will be uninstalled and weekly phone surveillance will be initiated. Three attempts will be made to contact subjects by phone and one attempt with a letter mailed to their street address. Subjects who cannot be reached by this method will be considered lost to follow up.

Subjects who report symptoms meeting the case definition of influenza (fever or feverishness plus either cough, rhinitis, or sore throat on the same or consecutive days) will be asked to return for an acute illness visit. At this visit the following procedures will take place

- Interval medical history will be obtained, including concomitant medications, reviewing any new events since the last visit.
- The presence and severity of respiratory symptoms will be assessed and recorded using a visual analog scale.
- A combined nasal and throat swab will be obtained for rtRT-PCR detection of influenza virus.
- If positive, the subject will be invited to participate in the Acute Flu study (DMID 14-0101) to assess the immune response to infection

8.3.6 Final study visit (Day 180 +/- 14 days)

Subjects will return approximately 180 days after vaccination for follow-up. This visit will be the study termination visit. At the final visit the following procedures will take place:

- Interval medical history will be obtained, including concomitant medications, reviewing any new events since the last visit
 - If indicated by medical history, a directed physical exam will also be performed.
 - Adverse events (AE) will be recorded and corrective actions taken if indicated
-

- A serum sample will be obtained from an arm vein for antibody titers
- Peripheral Blood Mononuclear Cells (PBMC) will be collected from an arm vein for assessment of the CD4 T cell response to vaccination

8.4 Early Termination Visit

If subjects discontinue from the study, they will be asked to make an early termination visit. At the time of the early termination visit, the reason for early termination will be recorded, current health status since the last visit will be reviewed, and all concomitant medications will be recorded. A targeted physical examination may be performed, as indicated, and information regarding AEs as described in the safety section 10.1 will be recorded.

Subjects will be encouraged to permit continued follow-up of AEs and to donate scheduled blood samples, if possible.

8.5 Unscheduled Visit

Unscheduled visits may occur at any time during the study. Any of the following activities may be performed:

- Medical history will be reviewed including concomitant medications, and updated as appropriate.
- All concomitant medications taken since the study visit will be recorded on the appropriate data collection form. Previously recorded medications will be updated as appropriate.
- Information regarding AEs as described in the safety section 10.1 will be recorded. .
- Depending on the reason for the unscheduled visit, vital signs, including oral or axillary temperature, pulse, and blood pressure, may be obtained.
- If indicated by medical history, a directed physical examination relevant to the interval medical history may be performed.
- Additional laboratory tests may be obtained depending on the nature of the unscheduled visit.

9 STUDY PROCEDURES AND EVALUATIONS

9.1 Clinical Evaluations

Medical History: Study personnel will take the medical history of all subjects. This history will include significant medical disorders of the head, eyes, ears, nose, throat, mouth, cardiovascular system, lungs, gastrointestinal tract, liver, pancreas, kidney, nervous system, blood, lymph glands, endocrine system, musculoskeletal system, skin, and genital/reproductive tract. It will also include a history of allergies, cancer, immunodeficiency, psychiatric illness, substance abuse, and autoimmune disease.

Medication History: Study personnel will record all medications, including prescription and over-the-counter drugs (such as vitamins, minerals, supplements, homeopathic preparations and/or therapies), taken by the subject in the 30 days prior to enrollment through 28 days after vaccination or early termination, whichever occurs first.

Medications that might interfere with the evaluation of the investigational product should not be used unless absolutely necessary. Medications in this category include, but are not limited to, glucocorticoids, i.e., oral, parenteral and high-dose inhaled steroids, and immunosuppressive or cytotoxic drugs. The administration of licensed vaccines should be delayed until 21 days after the study vaccine. Subjects should not receive experimental agents including vaccines for the duration of the study

Targeted Physical Examination: Licensed study clinicians (i.e., physician, physician's assistant, nurse practitioner) may conduct a targeted physical examination if indicated based on review of history for assessment of AEs that require VAERS reporting as described in section 10.1, or if necessary to assist in determining eligibility. All subjects will have vital signs (blood pressure, pulse, and oral temperature) and height and weight measured prior to vaccination.

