4.2 Outcome Measures

4.2.1 Primary Outcome Measures

The primary outcome measure for this study is:

- Mean change in the specificity, quantity and quality of serum antibody titers to the vaccine viruses, pH1N1, H3 and influenza B using HAI (year 1-5) and MN for pH1N1 and H3 viruses (years 1-5 from Day 0 to Day 28)

- Mean change in the CD4 T cell reactivity to pools of total pHA peptides derived from the pH1N1 HA, as well as H3, influenza B HA, NP, and M1 peptides will be quantified using cytokine Elispot From Day 0 to Day 14

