6.2 Exclusion Criteria

Subjects who meet any of the following exclusion criteria at baseline cannot participate in the study:

1. Subject report of known hypersensitivity to allergy to components of the study vaccine or other components of the study vaccine.
2. Subject report of a history of severe reactions following previous immunization with licensed or unlicensed influenza virus vaccines.
3. Subject report of a history of Guillain-Barre syndrome within 6 weeks of receipt of a previous influenza vaccine.
4. The subject is a woman who is pregnant or breastfeeding or intends to become pregnant during the study period between enrollment and 30 days following receipt of vaccine.
5. The subject is immunosuppressed as a result of an underlying illness or treatment with immunosuppressive or cytotoxic drugs, or use of anticancer chemotherapy or radiation therapy within the preceding 36 months.
6. The subject received immunoglobulin or another blood product within the 3 months prior to enrollment in this study.
7. The subject has an active neoplastic disease (excluding non-melanoma skin cancer or prostate cancer that is stable in the absence of therapy) or a history of any hematological malignancy. For this criterion, "active" is defined as having received treatment within the past 5 years.
8. The subject has long-term (greater than 2 weeks) use of oral or parenteral steroids

9. The subject has received an inactivated vaccine within the 2 weeks or a live vaccine within the 4 weeks prior to enrollment in this study or plans to receive another vaccine within the next 28 days.
10. The subject has an acute or chronic medical condition that, in the opinion of the investigator or appropriate sub-investigator, would render vaccination unsafe or would interfere with the evaluation of responses. These conditions include any acute or chronic medical disease or conditions defined as persisting for 3 months (defines as 90 days) or longer, that would place the subject at an unacceptable risk of injury, render the subject unable to meet the requirements of the protocol, or may interfere with the evaluation of responses of the subject's successful completion of the study.

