9.2 Laboratory Evaluations/Assays

9.2.1 Immunogenicity Evaluations

Serum hemagglutination-inhibition (HAI). HAI will be performed in microtiter format using turkey RBCs and egg-grown, betapropiolactone-inactivated A/California/07/09 virus as antigen. The titer of antibody will be defined as the highest dilution resulting in complete inhibition of hemagglutination. Sera will be treated with receptor-destroying enzyme and heat inactivated prior to testing at an initial starting dilution of 1:4. Sera with no detectable HAI titer will be assigned a titer of 1:2 for calculation purposes.

Microneutralization (MN) assay: Sera will be tested by microtiter technique for neutralization of an A/California/07/09 x PR8 reassortant virus in MDCK cells. Viral growth will be determined by ELISA of the cells following fixation with methanol using a combination of M- and NP-specific monoclonal antibodies. The titer of antibody will be defined as the highest titer resulting in 50% inhibition of antigen signal compared to un-neutralized control wells. Sera will be treated with RDE and heat inactivated prior to testing at an initial starting dilution of 1:10. Sera with no neutralizing titer will be assigned a value of 1:5 for calculation purposes.

B cell responses: Peripheral Blood Mononuclear Cells (PBMC) will be obtained before and on day 7 and 28 after vaccine and evaluated for B-cell responses. B cell responses will be evaluated by memory cell assay [16] and antibody secreting cell assay. In addition, B cells will be cultured in vitro and the functional quality of secreted antibody assessed by HAI and MN assays

CD4 T cell responses: PBMCs collected prior to and on day 3, 7, 14 and 180 after vaccination will be evaluated for the presence of antigen specific CD4 cells by ELISPOT assay and flow cytometry using a panel of peptides spanning the H1 hemagglutinin, neuraminidase and internal virion proteins such as NP and M1 [17]. This assay will identify both cross reactive and H1 specific epitope responses, as well as recall of memory cells to conserved internal virion proteins. PBMC will also be evaluated for the presence of antigen specific ELISPOT and cell homing markers by flow cytometry.

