12.2 Sample Size Considerations

The power analysis is based on the primary aim of comparison of serum antibody, specificity, memory B cell derived polyclonal antibodies (MpAb) and HA-specific CD4 T cell counts (in log scale to stabilize variance) between the group of subjects vaccinated with egg derived TIV IM and the group of subjects vaccinated with Baculovirus derived TIV IM. In this explorative study, the HA-specific CD4 T cell response to the Baculovirus derived vaccine is unknown and thus no information is available about the group difference. But our past experience indicated the coefficient of variation (CV) of HA-specific CD4 T cell counts varied between 0.25 and 0.4 [18]. If we assume CV and use percent-change differences in HA-specific CD4 T cell counts relative to the group with egg derived vaccine, with 45 subjects per group, we will have 80% power to detect at least 10% ~ 20% difference in HA-specific CD4 T cell counts between the two groups. This power analysis is based on two-sample t test with a two-sided significance level of 0.05 and equal allocation of subjects to any two groups.

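### Section 9.1 lifts the delay on other licensed vaccines at Day 21, a week before the Day 28 antibody and B-cell draw that the delay should protect

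*Combined protocol and SAP*

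**What the plan says.** Section 9.1 (Clinical Evaluations), in the paragraph on medications that could interfere with evaluation, states: "The administration of licensed vaccines should be delayed until 21 days after the study vaccine". It makes no distinction by type of vaccine.

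The other relevant provisions of the combined protocol and SAP are:

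- **Section 4.2.1 (Primary Outcome Measures).** The antibody outcome is a mean change in titre, with the interval given as "years 1-5 from Day 0 to Day 28".
- **Section 8.3.4 (Day 28 visit, window ± 2 days).** "A serum sample will be obtained from an arm vein for antibody titers". PBMC for the B-cell response are taken at the same visit.
- **Section 9.2.1 (Immunogenicity Evaluations).** PBMC are "obtained before and on day 7 and 28 after vaccine and evaluated for B-cell responses", using memory-cell and antibody-secreting-cell assays.
- **Section 6.2, exclusion 9.** A subject is excluded who "plans to receive another vaccine within the next 28 days". Section 8.2 has the entry criteria checked again at vaccination.
- **Section 7.6 (Concomitant Medications/Treatments).** "Receipt of a licensed vaccine" is one of the items reviewed at each follow-up visit and, if it has occurred, noted in the subject's record.
- **Section 12.4 (Final Analysis Plan).** No rule is given for samples taken after another vaccine.

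**The concern.** The evident purpose of the 21-day delay is to keep other vaccines from disturbing the immune readouts. It ends before the readout for the primary antibody outcome. The plan's own horizon for planned vaccines is 28 days, and it does not explain why an unplanned one should have a shorter limit.

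At stake are a few Day 28 serum and B-cell samples taken within days of a second vaccination, with no agreed way to handle them. The B-cell samples are the less certain part. The protocol itself samples B cells 7 days after the study vaccine, so it treats about one week as a relevant time for a vaccine-induced response. A vaccine given on Day 21 puts the nominal Day 28 draw at that same interval after a different product.

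**Working it through.** **Inputs**

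- Earliest day the delay allows another licensed vaccine: Day 21 (Section 9.1).
- Day 28 draw: Day 26 to Day 30 (Section 8.3.4, ± 2 days).
- Planned group size: 45 (Section 12.2, "with 45 subjects per group").
- Number of subjects receiving another vaccine between Day 21 and the draw: not given.
- Effect of such a vaccine on the assays: not given.

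**Step 1: gap between a Day 21 vaccine and the draw**

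Gap = day of draw − 21.

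| Draw on | Gap |
|---|---|
| Day 26 | 26 − 21 = 5 days |
| Day 28 | 28 − 21 = 7 days |
| Day 30 | 30 − 21 = 9 days |

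A vaccine given after Day 21 falls closer to the draw.

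**Step 2: does other text close the gap?**

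- Exclusion 9 is an entry criterion about what the subject plans. With the Day 0 re-check it removes vaccinations already planned, but it does not govern a vaccine that is offered or needed later. It screens at entry and Section 9.1 governs later conduct, so the two rules do not strictly contradict each other.
- Section 7.6 has receipt noted. It neither prohibits the vaccine nor says what happens to the sample.
- Section 12.4 is silent.

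An unplanned vaccine between Day 21 and the draw is therefore consistent with the protocol text. The Manual of Procedures and SOPs were not available and might say more.

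**Step 3: which endpoints are exposed?**

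- Day 28 HAI and MN titres: exposed, but these assays are virus-specific.
- Day 28 memory-cell and antibody-secreting-cell assays: exposed. Section 9.2.1 does not fully state their antigen specificity, so the effect is uncertain.
- Day 0 to Day 14 CD4 ELISPOT outcome: not exposed, because Day 14 precedes Day 21.

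**Step 4: illustration of size**

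Suppose *k* of 45 subjects each have a titre shifted two-fold. The group geometric mean titre is then multiplied by 2^(k/45):

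| *k* | 2^(k/45) | Shift |
|---|---|---|
| 1 | 1.016 | 1.6% |
| 2 | 1.031 | 3.1% |
| 4 | 1.064 | 6.4% |

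Both the two-fold shift and the values of *k* are assumptions. With no cross-effect the shift is 0% for every *k*.

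**Step 5: which limit closes the gap?**

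A fixed 28-day delay, matching exclusion 9, leaves 30 − 28 = 2 days when the visit falls on Day 30. A delay tied to the draw itself leaves 0 days wherever the visit falls in its window.

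**The case against.** The strongest counter-argument is that the mechanism is weak. HAI and MN use named influenza viruses, Section 8.2 describes the baseline PBMC as serving influenza-specific B-cell and CD4 assessment, and nothing in the documents suggests that an unrelated vaccine would alter those readouts. A second influenza vaccine could matter, but there is no reason to expect one three to four weeks after the study dose. Exclusion 9 already removes planned vaccinations and Section 7.6 captures the rest. No reason is apparent why unplanned vaccines should differ by arm, so no directional bias is shown.

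Most of this stands, and it limits the point to a minor one. It does not remove the gap: Section 9.1 names Day 21 as acceptable, and the specificity of two of the Day 28 B-cell assays is not fully stated. That the sentence is advisory does not help, because staff who follow it will allow a vaccine before the draw.

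A second objection is that Section 12.4 also allows the maximum post-vaccination value as an endpoint. Serum is drawn at Day 28 and Day 180, so a vaccine given between those visits could enter that maximum over a much longer period. This is fair, and the present point does not cover that interval. A disturbed Day 28 value can still enter both the Day 0 to Day 28 change and the maximum, so protecting that draw remains worthwhile.

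**Conclusion.** The concern holds as a minor design improvement. The on-study delay ends 5 to 9 days before the draw that supplies the primary antibody outcome and the Day 28 B-cell data, it is shorter than the plan's own 28-day horizon, and affected samples have no analysis rule.

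The effect on HAI and MN is probably small, and the effect on the Day 28 B-cell assays is uncertain. The true bias cannot be calculated from the documents. The 1.6% to 6.4% range depends wholly on an assumed two-fold shift and assumed counts of 1 to 4 in a group of 45. The timing conclusion needs only the stated visit days, and assumes that the Manual of Procedures and SOPs set no stricter limit.

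**What to change.** Make three small changes:

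1. **Section 9.1.** Replace the 21-day limit with: *Other licensed vaccines should be deferred until the Day 28 blood sample has been taken, unless medically urgent.*
2. **Section 7.6.** Where receipt of a licensed vaccine is already reviewed, record the product and the date.
3. **Section 12.4.** Flag any subject who received another vaccine between Day 0 and the Day 28 draw, and repeat the Day 28 antibody and B-cell analyses without them as a sensitivity analysis.

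The cost is one sentence of revised wording, a product and date entry at a review that already takes place, and one extra analysis. Non-urgent vaccines wait a further 5 to 9 days. The urgency exception protects subjects who need a vaccine sooner. Vaccines given between Day 28 and Day 180 would need a separate decision.
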